2.3.1 Primary Objectives

- To determine the maximum tolerated dose (MTD) and identify the recommended Phase 3 dose (RP3D) and schedule of oprozomib in combination with pomalidomide and dexamethasone (OPomd) in subjects with primary refractory or relapsed and refractory multiple myeloma
- To evaluate the safety and tolerability of the OPomd combination in subjects with primary refractory or relapsed and refractory multiple myeloma

2.3.2 Secondary Objectives

- To estimate the overall response rate (ORR) of OPomd, defined as the proportion of subjects with an overall response of stringent complete response (sCR), complete response (CR), very good partial response (VGPR), or partial response

(PR) as determined by investigator according to the International Myeloma Working Group- Uniform Response Criteria (IMWG-URC)

- To estimate the clinical benefit rate (CBR) of OPomd, defined as the proportion of subjects with an overall response of minimal response (MR) or better as determined by investigator according to the IMWG-URC and modified European Group for Blood and Marrow Transplantation (EBMT) criteria
- To characterize the pharmacokinetics (PK) of oprozomib in the OPomd regimen

2.4 Sample Size Justification

Part 1: Phase 1b Dose-Escalation and Dose-Expansion Portions of the Study

A total enrollment of approximately 82 subjects is planned for Part 1 of the study. During the Part 1 Phase 1b dose-escalation portion of the study, approximately 21 subjects are expected to be enrolled for each schedule. The estimated sample size for the dose-escalation part of the study is based on standard 3 + 3 dose-escalation rules, with expectations that 2–3 dosing cohorts of 3–6 subjects per cohort will be required to establish the MTD. A minimum of 6 subjects must be treated at the MTD. For each schedule, more than 1 MTD for oprozomib may be established if additional dose levels of pomalidomide are assessed. The MTD for oprozomib in combination with each dose level of pomalidomide will be the dose(s) where < 2 DLTs in 6 subjects are observed.

The actual number of required subjects will depend on both the total number of cohorts, and the need to expand a given cohort from 3 to 6 subjects in order to identify the MTD. Properties of the dose-escalation rules for different underlying DLT rates are provided in Table 1.

Table 1 Properties of the Dose-Escalation Rules for Different Underlying DLT Rates

| Underlying Rate of DLT | Probability of Enrolling 3 Additional Subjects | Probability that Dose is Determined to be |
|------------------------|--|---|
|------------------------|--|---|

| | | Tolerated |
|------|------|-----------|
| 0.10 | 0.24 | 0.91 |
| 0.20 | 0.38 | 0.71 |
| 0.33 | 0.44 | 0.43 |
| 0.40 | 0.43 | 0.31 |
| 0.50 | 0.38 | 0.17 |
| 0.60 | 0.29 | 0.08 |

DLT = dose-limiting toxicity.

The criteria for selecting the RP3D for each schedule at the sponsor's discretion will include assessment of the safety, tolerability, and preliminary activity of oprozomib observed across multiple cycles. In addition, both PK and PDn assessments to demonstrate adequate exposure and proteasome inhibition will be a key factor. The CSRC will review the data and provide guidance in selection of the RP3D. Therefore the RP3D may differ from the MTD, but will not be higher than the MTD. A minimum of 20 additional subjects are planned for enrollment and treatment for 1 or both schedules at the sponsor's discretion at the RP3D during the Phase 1b dose-expansion portion of Part 1 of the study. In the dose-expansion portion of the study, if the true ORR $\geq 40\%$, then the probability of seeing at least 7 responses among the 26 subjects (6 treated at the MTD during escalation + 20 in the expansion) is approximately 94%.

3 STUDY ENDPOINTS

3.1 Primary Endpoints

Part 1:

- DLTs
- Adverse events and laboratory abnormalities graded according to NCI-CTCAE, Version 4.03
- Vital signs and clinical laboratory results during and following study drug administration

3.2 Secondary Endpoints

Part 1:

- Overall response, defined as the best response of sCR, CR, VGPR, or PR, as determined by investigator according to the IMWG-URC
- Clinical benefit, defined as defined as the best response of MR or better, as determined by investigator according to the IMWG-URC and modified EBMT criteria
- Pharmacokinetic parameters, including maximum plasma concentration (C_{max}), time to maximum concentration (T_{max}), area under the plasma concentration time curve from time 0 to last time point ($AUC_{0-\tau}$), and area under the plasma concentration time curve from time 0 to time infinity ($AUC_{0-\infty}$) using noncompartmental methods

4 ANALYSIS POPULATIONS

All subjects who receive at least 1 dose of study treatment in Part 1 of the study will be considered evaluable for both the efficacy and safety analyses (Safety Population). The Safety Population will be the primary population for all safety and efficacy data presented.

5 ANALYTIC DEFINITIONS

5.1 Study Day 1

Study day 1 corresponds to the date of the first dose of study drug.

5.2 Study Day

For events, assessments, and interventions after study day 1, study day represents the elapsed number of days from study day 1, inclusive:

$$\text{Study Day } n = (\text{Date of assessment} - \text{Date of Study Day 1}) + 1 \text{ day}$$

Unless otherwise specified, the timing of all study-related events, assessments, and interventions will be calculated relative to study day 1. Study day -1 will be the day before study day 1, and in general for assessments prior to study day 1, study day is defined as:

$$\text{Study Day } n = (\text{Date of assessment} - \text{Date of Study Day 1})$$

For listings (such as for adverse events) that include the derivation of “days since last dose,” this is defined as event date – date of last dose. Events that occur on the same day as the last dose of study drug will therefore be described as occurring zero days from the last dose of study drug.

5.3 Baseline

Unless otherwise specified, the baseline value is defined as the last assessment prior to the first dose of OPZ, POM or DEX.

6 INTERIM ANALYSIS AND EARLY STOPPING GUIDELINES

There are no formal interim analyses planned for this study. A Cohort Safety Review Committee (CSRC) will review the clinical and laboratory data of each dose cohort before escalating the OPZ dose to the next dose cohort.

7 STATISTICAL METHODS

7.1 General Considerations

This statistical analysis plan is being generated prior to locking the study database. It specifies the main efficacy and safety analyses to be performed.

All statistical summaries and analyses will be performed in SAS[®] version 9.3 or higher (SAS Institute Inc., Cary, NC, USA) on a PC platform.

In general, summaries of all data will be presented by schedule and dose groups, defined as initial dose level cohort for phase 1 and recommended dose cohort for phase 2. In addition, some summaries will include the combined recommended dose cohort from phase 1 and 2 and total cohorts (all subjects by schedule).

Summary statistics will be provided for selected endpoints. For continuous variables, the number of subjects with non-missing data (n), mean, standard deviation, median, minimum, and maximum will be presented. For discrete data, the frequency and percent distribution will be presented. Unless otherwise indicated, percentages will be calculated based upon the number of subjects in the Safety Population in each dose group as the denominator.

Confidence intervals, when presented, will be constructed at the 95% level. For binomial variables, exact distribution methods will be employed. The distribution of time-to-event endpoints will be summarized by Kaplan-Meier method. Quartiles including median will be estimated by Kaplan-Meier method along with their 95% confidence intervals.

Individual subject data recorded on the electronic case report forms (eCRFs) and any derived data will be presented by dose cohort and subject in data listings.

7.2 Disposition of Subjects

The following subject disposition information will be summarized for all subjects by each of the schedule and dose group and for the combined dose groups (total group).

- number of treated subjects
- number (%) of subjects who discontinue from the study drug
- primary reason for study drug discontinuation
- number (%) who had an End of Study visit
- reason for no End of Study visit

7.3 Demographic and Baseline Characteristics

7.3.1 Demographic and Baseline Characteristics

The following demographic and baseline characteristics will be summarized for the Safety Population.

- Age (years) and age categorized (years) as <65, 65 - <75, and ≥ 75
- Sex
- Ethnicity
- Race
- Baseline ECOG performance status
- Baseline fertility status
- Baseline weight (kg)
- Baseline height (cm)

7.3.2 Disease Characteristics

The following disease characteristics will be summarized for the Safety Population.

- ISS at initial diagnosis and at Screening
- Time (years) since initial diagnosis, defined as date of informed consent signed

minus date of diagnosis

- Category of multiple myeloma
- Heavy chain and light chain status
- Plasma cell involvement (%) as assessed with bone marrow assessment (< 50%, ≥ 50%, unknown or missing)
- FISH (standard risk, high risk, unknown or not done)
 - High risk: with one of the following abnormalities: t(4;14), t(14;16), del(17p;13), or 1q21 amplification
 - Standard risk: none of the high risk finding
- Baseline β 2 microglobulin (mg/L) (< 5.5 mg/L versus \geq 5.5 mg/L)

7.3.3 Prior Cancer Therapies

The following prior cancer therapy data will be summarized for the Safety Population:

- Number (%) of subjects with at least one prior:
 - Chemotherapy
 - Transplant
 - Radiotherapy
 - No prior therapy
- Number of regimens of prior treatment (1, 2, etc) for multiple myeloma and number of prior drugs

7.4 Treatments and Medications

7.4.1 Study Drug Administration

The overall extent of study treatment exposure and dose information will be summarized for the Safety Population for OPZ, POM and DEX.

- Duration of treatment (weeks), defined as (date of last dose – date of first dose + 1) divided by 7 for OPZ, POM and DEX
- Total number of treatment cycles during which one full daily dose of OPZ, POM and DEX was taken by the subject.
- Number (%) of subjects dosed by cycle, where a subject will be considered to have been dosed in a cycle if the subject receives at least one full daily dose of OPZ, POM and DEX.
- Total doses received across all cycles of OPZ, POM and DEX
- Dose modifications of study drug based on AE action taken data

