#### 14.4.1 TREATMENT EXPOSURE AND MEDICATION COMPLIANCE

Extent of exposure to all study treatments (oprozomib, pomalidomide, and dexamethasone) will be evaluated by summary statistics (N, mean, standard deviation, median, and range). Percentage of subjects and cycles with dose delays and reductions will be calculated by treatment group.

The dose intensity of oprozomib, pomalidomide, and dexamethasone (ie, the amount of drug delivered to a subject per week of treatment) will be calculated according to standard methodology (Hryniuk, 1990; Longo, 1991) that accounts for treatment delays on the calculated dose intensity result. For each subject, the relative dose intensity (actual versus planned) of each treatment will be calculated. The average relative dose intensity for each treatment group will be calculated by summarizing the average relative dose intensity for individual subjects. The results for pomalidomide and dexamethasone will be provided to determine the presence of any major differences between the treatment groups for the planned versus actual dose and schedule of these two (2) study medications.

Approved

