1 INTRODUCTION

This statistical analysis plan (SAP) was prepared for an abbreviated clinical study report (aCSR) for the Part 1 of the study in accordance with Protocol OPZ007, dated 08 July 2014 (amendment 2), and describes the analyses of data collected within the scope of the Part 1 of the study. Any changes that are made to the planned analyses after the SAP is finalized, along with an explanation as to when and why they occurred, will be noted in the aCSR produced for the study. Any changes made to the planned analyses that are in the protocol will be identified and documented in this document.

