7.6.3 Vital Signs and Weight

Vital sign results including blood pressure, pulse, and temperature will be included in the subject data listings.

7.6.4 12-Lead Electrocardiogram

Maximum post-baseline and maximum increase from baseline categories of corrected QT interval results will be summarized.

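### SAP 7.4.1 omits the protocol's relative dose intensity and delay/reduction rates, and SAP 7.6.3 only lists vital signs; neither departure is documented

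*SAP*

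**What the plan says.** **Exposure, protocol.** Section 14.4.1 plans dose intensity for oprozomib, pomalidomide and dexamethasone, with delays taken into account. It adds: "For each subject, the relative dose intensity (actual versus planned) of each treatment will be calculated". It also says: "Percentage of subjects and cycles with dose delays and reductions will be calculated by treatment group".

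**Exposure, SAP.** Section 7.4.1 lists five items:
- treatment duration, from "date of last dose – date of first dose + 1) divided by 7"
- the number of cycles with one full daily dose
- subjects dosed by cycle, where a subject counts as "dosed in a cycle if the subject receives at least one full daily dose of OPZ, POM and DEX"
- total doses received
- "Dose modifications of study drug based on AE action taken data"

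Dose intensity, RDI and the percentage of cycles with delays or reductions do not appear. SAP 7.1 groups dose-escalation subjects by their initial dose level.

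**Vital signs.** Both documents name as a primary endpoint "Vital signs and clinical laboratory results during and following study drug administration". Protocol 14.5.3 says safety will be assessed through summaries, and vital signs are among the items named. SAP 7.6.3 says only: "Vital sign results including blood pressure, pulse, and temperature will be included in the subject data listings". Laboratory and ECG data do get summaries (SAP 7.6.2 and 7.6.4).

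**Documentation.** SAP section 1 says: "Any changes made to the planned analyses that are in the protocol will be identified and documented in this document". The SAP records neither departure.

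**The concern.** Tolerability is a primary objective, and the recommended dose is to rest on what is seen over several cycles. A cohort's tolerability depends on how much of the assigned dose its subjects could take. RDI answers that directly, and the protocol planned it for all three drugs. Without it, the report has no measure that sets delivered dose against planned dose, and reduced subjects stay in the column of the dose they started on.

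Drawing dose modifications only from AE records also narrows the protocol's measure. The protocol foresees at least three kinds of change with no AE behind them:
- dexamethasone lowered to 10 mg over age 75 at the investigator's discretion (10.4.1)
- weeks missed for reasons other than toxicity (10.4.1)
- intrasubject escalation to the recommended dose (5.1.3)

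The vital-signs gap is a separate matter: part of a primary endpoint would reach the report with no tabulation. Orthostatic change is the obvious loss. Grade 3 orthostatic hypotension was a DLT with single-agent oprozomib (3.5.1), the protocol gives it its own management guidance (10.6.1.8), and supine and standing readings are taken before and after dosing in Cycle 1.

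**Working it through.** The plan states no figure to reproduce here. The check asks what each SAP 7.4.1 measure would show for dose changes that the protocol itself sets out.

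**Inputs.** Planned doses per 28-day cycle: oprozomib 10 (5/14) or 8 (2/7), pomalidomide 21, dexamethasone 8. Reduction steps come from Tables 9 to 12 in protocol 10.4.1.

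**Formula.** RDI per cycle = (delivered doses × delivered mg) / (planned doses × planned mg).

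| Change | Planned mg | Delivered mg | RDI | Doses taken |
|---|---|---|---|---|
| Oprozomib 5/14, 210 to 150 mg, same days | 10 × 210 = 2100 | 10 × 150 = 1500 | 71% | 10 of 10 |
| Oprozomib 2/7, 210 to 150 mg, same days | 8 × 210 = 1680 | 8 × 150 = 1200 | 71% | 8 of 8 |
| Pomalidomide 4 to 1 mg | 21 × 4 = 84 | 21 × 1 = 21 | 25% | 21 of 21 |
| Dexamethasone 20 to 10 mg | 8 × 20 = 160 | 8 × 10 = 80 | 50% | 8 of 8 |
| Oprozomib 5/14, 150 mg moved to 3/14 | 10 × 150 = 1500 | 6 × 150 = 900 | 60% | 6 of 10 |
| Oprozomib 5/14, 210 to 150 mg and 3/14 | 2100 | 6 × 150 = 900 | 43% | 6 of 10 |
| Oprozomib 2/7, 210 to 150 mg and 1/7 | 1680 | 4 × 150 = 600 | 36% | 4 of 8 |

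The dexamethasone row takes 20 mg as the plan. Table 12 treats 10 mg as a nominal dose for subjects over 75 from Cycle 2, so the reference dose has to be stated.

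**Six cycles on 5/14 from 210 mg, reduced from Cycle 2.** Planned: 6 × 2100 = 12,600 mg in 60 doses.
- *150 mg, same days:* 2100 + 5 × 1500 = 9600 mg, RDI 76%, 60 of 60 doses. The last dose falls on day 5 × 28 + 19 = 159, as planned, so duration is 159/7 = 22.7 weeks either way.
- *150 mg on 3/14:* 2100 + 5 × 900 = 6600 mg, RDI 52%, 10 + 5 × 6 = 40 of 60 doses. The last dose falls on day 5 × 28 + 17 = 157, or 22.4 weeks.

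**What each measure shows.**
- *Duration* is identical or nearly so in both cases.
- *Total doses* has no stated unit and no planned denominator. As a count it misses the first case entirely but falls by a third in the second. As milligrams it would fall in both, still with nothing to compare it with.
- *Cycles dosed* depends on what a full daily dose is. If it is the currently assigned dose, reduced cycles count. If it is the originally planned dose, the 210-to-150 mg cycles drop out. The 150 mg subject moved to 3/14 counts for oprozomib on either reading.
- *AE action taken* should catch toxicity-driven steps. It need not catch the three non-AE changes. The default denominator in SAP 7.1 is subjects, so it gives no percentage of cycles.

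**Does an amendment explain the omission?** The SAP is written to Amendment 2. That amendment's summary of changes removed a separate compliance measure from 14.4.1 but kept RDI. Amendment 3's summary lists no change to 14.4.1, and it carries the vital-signs sentence in 14.5.3 over intact.

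**The case against.** A reader might infer that, under this SAP, heavily reduced dosing would look like full exposure. The documents do not support that. Total doses received would fall whenever days are skipped, to 6 of 10 or 4 of 8 per cycle at the deepest steps above. The steps in Tables 9 and 10 respond to toxicity, and action taken must be recorded for every AE (protocol 13.3.1), so most reductions should be visible there. Subject listings remain. All of this stands; what stays hidden from the summaries is the ratio of delivered to planned dose, the per-cycle rates, and changes with no AE.

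Other tempting readings also go too far:
- That a cycle counts only if all three drugs were taken. The same three-drug phrase elsewhere in SAP 7.4.1 plainly means each drug, so this is an ambiguity to remove.
- That AE records would count one reduction several times. With subjects as the denominator, this is not established.
- That listing vital signs distorts exposure. It does not. Orthostatic hypotension reported as an AE or DLT would still appear in those outputs.

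The sponsor could add that the SAP serves an abbreviated report after Part 2 was cancelled, that the dose was chosen during conduct with the safety committee, and that 14.4.1 ties part of the dose-intensity reporting to comparing treatment groups. This weakens any claim that dose selection was harmed. It does not remove the protocol's commitment for each drug. SAP 2.1 also gives GI tolerability and PK variability as reasons for reformulating, so delivered dose still matters to readers of the report.

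**Conclusion.** The point holds as two undocumented departures from the protocol, both worth correcting.

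On exposure, the SAP leaves no actual-versus-planned measure and no per-cycle delay or reduction rate, and its source for dose modifications can miss changes the protocol foresees without an AE. The size depends on the type of change. A milligram reduction on unchanged days can mean 71% RDI for oprozomib, or 25% for pomalidomide at its lowest step, with unchanged duration and a complete dose count. This assumes total doses is a count. The direction of any error in the cycle counts cannot be settled until a full daily dose is defined. The percentages illustrate the protocol's own tables; they do not predict how many subjects would be affected.

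On vital signs, part of a primary endpoint is left without the summary that protocol 14.5.3 calls for. This is independent of the exposure question.

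The documents do not show that reduced subjects would pass as fully exposed, or that the recommended dose was chosen on faulty tables.

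**What to change.** **SAP 7.4.1.** For each drug, calculate from dosing records the cumulative dose in mg, dose intensity, RDI, and the percentage of subjects and of cycles with any delay, omission or reduction, by schedule and cohort. State the planned dose used as the reference, including for subjects over 75 on dexamethasone and after intrasubject escalation. Define a full daily dose, and what counts as dosed in a cycle, separately for each drug. Give the unit of total doses. Keep the AE action-taken table as a supplement.

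**SAP 7.6.3.** Add a descriptive vital-signs summary by schedule and cohort, including the supine-to-standing change already measured under protocol 11.1.1. An incidence table using that section's definition of an orthostatic drop would be useful but goes beyond what 14.5.3 requires.

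**SAP section 1.** Record and justify any protocol analysis that is still dropped.

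**Cost.** SAP wording and a few descriptive tables. Sites already document dosing compliance for all three drugs (protocol 9.4), and orthostatic readings are already part of every vital-sign assessment, so no new data are needed.

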7.5 Efficacy Analyses

All efficacy analyses will be based on the Safety Population. Disease progression as collected at the end of treatment (end of study visit) as determined by the investigator will be used for the analysis for DOR.

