### **16.1.1 Protocol and Amendments**

Protocol Amendment 3, dated 07 March 2018 was generated and approved. Shortly thereafter, a decision was made to terminate the study program, the amendment was not implemented. The last version of the protocol, under which the study was active, was Amendment 2, dated 2014 March 20.

Onyx Therapeutics  
Oprozomib ER Tablets

Clinical Study Protocol No. OPZ007  
Page 1 of 223

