7.5.2 Duration of Response

Duration of response (DOR) will be calculated for subjects who achieve a sCR, CR, nCR, VGPR, or PR. For such subjects, the duration of overall response is defined as the time from first evidence of PR or better to disease progression or death due to any cause.

$$DOR = \text{Earliest date of disease progression, death, or censoring} - \text{Date of first observation of PR or better before confirmation} + 1 \text{ and expressed in months}$$

Duration of response will be right-censored for subjects who at least achieve a PR based on the censoring conventions defined previously for PFS. Analysis of DOR will be performed using the Kaplan–Meier method. Medians and other quartiles for DOR will be estimated in addition to the corresponding 2-sided 95% confidence intervals.

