7.7 Handling of Dropouts or Missing Data

The handling of dropouts and missing disease status assessments for the efficacy variables is described in their definitions.

Missing or partially missing dates will not be imputed at data level. However, assumptions for missing or partially missing dates for important variables will be made to allow inclusion of appropriate data records in the analyses.

If a medication date or time is missing or partially missing, so it cannot be determined whether it was taken prior or concomitantly, it will be considered as a prior, concomitant, and a post-treatment medication.

If the partial AE onset date information does not indicate whether the AE started prior to treatment or after the TEAE period, the AE will be classified as TEAEs.

If the start day of subsequent anti-cancer therapy is missing, it will be assumed to be the first day of the month.

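### SAP 7.5 ties progression for duration of response to the end-of-treatment visit, at odds with SAP 7.5.2 and the Amendment 2 follow-up, and the censoring rule that 7.5.2 points to is not in the SAP

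*SAP*

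**What the plan says.** SAP 7.5.2 computes DOR for responders, from the first evidence of PR or better to progression or death from any cause. It plans Kaplan-Meier medians and other quartiles with two-sided 95% confidence intervals. Nothing in that definition limits the visit at which progression may be found.

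SAP 7.5, which introduces the efficacy analyses, names a source of progression for the same endpoint: "Disease progression as collected at the end of treatment (end of study visit) as determined by the investigator will be used for the analysis". The sentence ends by naming DOR, and no other source is given.

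On censoring, SAP 7.5.2 says DOR is right-censored "based on the censoring conventions defined previously for PFS". On missing assessments, SAP 7.7 says: "The handling of dropouts and missing disease status assessments for the efficacy variables is described in their definitions". SAP 7.7 adds: "If the start day of subsequent anti-cancer therapy is missing, it will be assumed to be the first day of the month".

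The protocol text supplied is Amendment 3, which was approved but not implemented. Protocol 16.1.1 states: "The last version of the protocol, under which the study was active, was Amendment 2". SAP Section 1 says that the plan follows Amendment 2.

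**The concern.** Take a responder who stops treatment for toxicity while still in response and is found to have progressed some months later, at a scheduled follow-up assessment. Under SAP 7.5.2 that is a DOR event. Under SAP 7.5, read literally, it is not, because it was not collected at the visit named. The SAP does not say what happens to this subject instead: censored at end of treatment, or kept at risk with only death counted. The two treatments can give different medians.

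The censoring rule should settle this, but the SAP refers to one it does not contain. Two programmers working from the same data could report different medians and intervals, and both could claim to have followed the plan.

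**Working it through.** **Step 1: which follow-up applied.** Section 12.3 as printed (Amendment 3) drops disease assessment after treatment. The Amendment 2 wording, in the changed-from column of Appendix Q, has subjects without progression at end of study treatment assessed every 4 weeks through 18 months on study, then every 8 weeks from Month 20, until progression or next therapy. Protocol 10.1 (follow-up to progression once both drugs stop) and Appendix A1 footnote n agree. Amendment 2 is used here because the study ran under it and the SAP was written to it. (Protocol 16.1.1 dates it 2014 March 20 and the SAP 08 July 2014; nothing here depends on that.)

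**Step 2: the passages side by side.**

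| Question | SAP 7.5 | SAP 7.5.2 | Protocol |
|---|---|---|---|
| Where may progression be found? | End-of-treatment (end of study) visit | No limit | On treatment and in follow-up; progression has its own eCRF (13.3.2) |
| When is that visit? | Not defined | Not defined | End of Study Treatment assessments fall within 30 days of last dose (Section 12) |
| How is DOR censored? | Not stated | By PFS conventions | 14.6 refers to the SAP |

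**Step 3: following the censoring references.** SAP 7.5 goes from 7.5.1 (response rate) straight to 7.5.2 (DOR), and the contents list shows no PFS section. Protocol 14.6 sends DOR censoring to the SAP. SAP 7.7 sends missing assessments back to the endpoint definitions. SAP 7.7 also completes the start day of subsequent anticancer therapy, yet no SAP rule uses that date. The only PFS censoring table in the documents is Amendment 2 Table 18. It was written for the cancelled Phase 3 part, runs from randomization, and is not cited in the SAP.

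**Step 4: scale.** The documents give no DOR figure. Their sample-size statement is at least 7 responses among 26 with probability about 94% if the true ORR is 40%. The binomial tail is P(X ≥ 7 | 26, 0.40) = 0.944, which agrees. At that design value, 26 × 0.40 = 10.4 responders per expanded schedule. If 20% to 40% stop without progression (assumption), 10.4 × 0.20 = 2.1 to 10.4 × 0.40 = 4.2 responders are affected.

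**Step 5: illustration, all rates assumed.** Exponential times throughout.

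*(a) Censored at end of treatment, later risk a multiple of the on-treatment risk.* With on-treatment hazard ln2/6, Kaplan-Meier under this censoring returns 6.0 months whatever happens later. Take 30% stopping without progression and a median of 2 months to next therapy. Counting follow-up events, censored at next therapy, then gives:

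| Later risk | Follow-up counted | Shift (6.0 minus it) |
|---|---|---|
| ×0.5 | 6.28 | −0.28 |
| ×1 | 6.00 | 0 |
| ×1.5 | 5.80 | +0.20 |
| ×2 | 5.63 | +0.37 |

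Over 72 scenarios (median 6 or 8 months; 20%, 30% or 40% stopping; next therapy at a median of 1, 2 or 4 months; follow-up 12 to 18 months) the shift ran from −0.74 to +0.83 months.

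*(b) Censored at end of treatment, stopping one month before progression.* With a true median of 8 months and 10% to 40% stopping, the estimate is 8.8 to 12.9. The range in (a) is therefore not a bound.

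*(c) Later progression ignored, later death counted.* With a true median of 8 months, 10% to 40% stopping and a median of 12 months from progression to death, the estimate is 8.3 to 10.7, upward throughout.

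**Step 6: precision.** With 10 uncensored exponential times, the interval from the 2nd to the 9th ordered time covers the median with probability 1 − 2(1 + 10)/2^10 = 0.979. Its expected limits are (1/10 + 1/9)/ln2 = 0.30 and (1/10 + … + 1/2)/ln2 = 2.78 times the true median. That is wider than any shift in Step 5.

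**The case against.** The strongest reply is that SAP 7.5 never says the visit is the only source. A reader might infer that the plan forbids progression found in follow-up, and the text does not go that far. The sentence may only be naming the investigator as assessor. Its parenthesis merges end of treatment with end of study, terms that Amendment 2 set out to distinguish, so it could even mean a visit after follow-up. The open definition in 7.5.2 and the separate progression eCRF also point towards using all progression. This stands as far as it goes: the sentence is unclear, and the exclusion follows only on its literal reading. It does not remove the need to reconcile 7.5 with 7.5.2.

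A second reply is that the missing censoring rule can be inferred. The SAP follows Amendment 2, which holds one PFS censoring table, and the therapy-date rule in SAP 7.7 fits that table's new-therapy row. That is a reasonable guess at intent and makes the gap easy to repair. It is still a guess, because the table is uncited and has a different time origin.

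Three further inferences should be resisted. The disposition row "reason for no End of Study visit" in SAP 7.2 does not show that such visits were expected to be missing. The documents show that follow-up was planned, not that any responder stopped without progression or progressed later. The simulated shifts do not estimate this trial's bias, since none of their rates comes from the documents.

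**Conclusion.** The point holds at minor severity. Followed as written, SAP 7.5 leaves out progression that SAP 7.5.2 counts and that the operative protocol required sites to look for. The DOR censoring rule is referred to but absent.

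Neither the size nor the direction of any bias can be derived from the documents. Under end-of-treatment censoring the bias is zero if stopping is unrelated to later risk, and can go either way if it is related. If later deaths count but later progression does not, the median is too long relative to 7.5.2. A reader might conclude that the reported median is necessarily inflated, but that depends on a censoring rule the SAP does not state.

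The consequence is limited. SAP 3.2 lists overall response ("Overall response, defined as the best response of sCR, CR, VGPR, or PR, as determined by investigator according to the IMWG-URC"), clinical benefit and pharmacokinetics as secondary endpoints; DOR is not among these or the primary endpoints. The protocol (Synopsis and 14.5.2) planned only a listing of DOR, and the SAP serves an abbreviated report.

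**What to change.** **SAP 7.5.** Replace the sentence with one saying that progression for DOR is the first investigator-assessed PD from any assessment, on treatment or in follow-up, confirmed as the protocol requires (including the cases where one measurement suffices) and dated at first observation.

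**SAP 7.5.2.** Replace the PFS cross-reference with an explicit rule. One candidate is Amendment 2 Table 18, with the clock starting at first PR or better:

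- Death or PD between planned assessments: event, at the earlier of death and the first assessment showing PD.
- Alive without PD: censor at the last disease assessment.
- New anticancer therapy before PD or death: censor at the last assessment before it.
- Death or PD directly after more than one missed assessment in a row: censor at the last assessment without PD before the first missed one.

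The new-therapy row is a choice and is not part of the 7.5.2 definition. The sponsor may intend another convention and should then write that one. Amendment 2 ended post-treatment disease assessments at next therapy, so a rule that keeps subjects at risk beyond it would rest largely on deaths.

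**Progression criteria.** Reconcile the starting M-component at which a rise of at least 1 g/dL suffices for progression: 0.5 g/dL in protocol 11.3, 5 g/dL in Appendix C, Table D1, note e. Otherwise the revised sentence in 7.5 still points to two criteria.

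**Cost.** SAP wording and minor reprogramming, using assessments that the operative protocol already required. The reported median may move in either direction. If the analysis has already been run, as the Amendment 3 rationale indicates, the abbreviated report should state which source of progression and which censoring rule were used.
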